#### **Effect of Treatment on the Treated Analysis**

Per-protocol analyses require adjusting for loss to follow-up and off-protocol therapies or treatments, but if group differences vary too greatly, model misspecification can yield biased estimates. Propensity score methods are an alternative. We will match intervention organization patients in three categories of tool use (never used during follow-up, used once, used more than once) to control organization patients. Counts of tool use will include use at index visit or subsequent study period visits, excluding the last visit. Matching variables will include age, FPL, outcome of interest at baseline, race / ethnicity, sex, count of ambulatory care visits post-index

visit, time from index visit to last study period visit, and clinic rural / urban status. Propensity scores will be estimated using nearest-neighbor matching with replacement.

As analyses in other settings indicated CV Wizard's potential for greater impact among patients with higher baseline risk, analyses of change in reversible risk will be stratified by baseline risk <10% or ≥10%. The assumption being that patients with lower baseline risk are less likely to improve. Additionally, we will run analyses by quartile of baseline reversible risk among patients for whom the tool was ever used during follow-up, matched to controls as described above. Analyses of change in reversible risk will include all patients meeting study inclusion / exclusion criteria; for other outcomes, analyses were restricted to patients with uncontrolled baseline risk. Linear mixed models will be used for all outcomes and checked for normality of residuals.

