### Programming CV Wizard to Accept OCHIN Data

Working with HealthPartners' programmers who previously disseminated CV Wizard to other large care systems, OCHIN's programmers will (1) build tables for data extraction (*e.g.*, medication, laboratory, diagnostic/problem list codes, vitals, smoking); (2) develop the interconnect routines needed to transmit EHR data to the CV Wizard web service, save response information in EHR flow sheets, and display the CDS results in the EHR; (3) create the alert to prompt CDS use in targeted patients; (4) develop "smart tools" (*e.g.*, dot phrases) to facilitate documenting CV Wizard use and results in EHR encounter notes; (5) program the dynamic order sets that are tailored to facilitate clinical actions recommended for each patient; (6) create CDS use rate feedback reports; and (7) develop a process to manage provider feedback on clinical aspects of CV Wizard.

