#### **Quantitative Data**

To be included in Aim 1 analyses a patient must have at least one visit in the 6 months after the Arm 1 implementation date at an Arm 1 or Arm 2 CHC and at least one additional visit at a study clinic in the 12-month post-index visit period. The first visit is referred to as the index visit. We will describe those who had inadequate follow-up data (did not have at least one additional visit in the post-index period). For each study subject, CVD risk score / risk factor management status will be calculated at index visit and each encounter during follow-up. While the tool can be run for patients of any age, we will restrict our analyses to patients 40-75 years of age.

We will test for between-group differences in baseline characteristics such as age, sex, race and ethnicity, insurance type, visit count, and health status using chi-square, t-test, and nonparametric Wilcoxon rank-sum tests as appropriate. We will also test for association between baseline characteristics and our outcomes of interest. We will examine the number of patients seen in each service area and clinic and each Arm and compare the characteristics of Arm 1 patients for whom the tool was used to those in Arm 1 for whom the tool was not used and to Arm 2 patients. Because the two arms were selected based on clinic size, percent of patients with a diagnosis for hypertension and the percent of patients that use tobacco, we anticipate there will be differences between the two groups resulting in the need to adjust for these differences. We will also examine characteristics at the service area and clinic-level in Arm 1 for whom the tool was used compared to Arm 1 service areas / clinics for whom the tool was not used and Arm 2 service areas / clinics.

Unadjusted trends in the monthly use and view rates for each of the study CHCs will be explored with use rates defined as: the number of encounters where CV Wizard was printed / number of targeted encounters with high-CVD risk patients per month and view rates defined as the number of encounters where CV Wizard was viewed / number of targeted encounters with high-CV risk patients per month.

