We will also examine overall rates of each of the impact outcomes (BMI in normal range, controlled blood pressure, controlled LDL, controlled HbA1c, and non-smoking status) pre/post tool use to assess any changes in patterns for patients in Arm 1 for whom the tool was used compared to those in Arm 1 for whom the tool was not used as well as to Arm 2 patients. The date the tool was first used for each patient will be assigned as the start of the post-period.

Extent of adoption of a CDS tool like CV Wizard directly impacts its population-level impact. To differentiate between the tool's population level impact versus impact when used, we will conduct intent to treat (ITT) analyses to compare all targeted patients at intervention versus control clinics. We will also conduct effect of treatment on the treated (ETOT; also called per protocol) analyses limited to intervention CHC patients for whom the CV Wizard tool was used (results viewed / printed out) at the index visit, compared to intervention clinic patients for whom it was not used, and separately, to control clinic patients. The ITT analyses test the hypotheses that targeted patients in intervention clinics will have significantly lower CVD risk scores and higher rates of CVD risk factor control, at visits in the year post-index visit period, compared to similar patients in control clinics. The ETOT analyses test the hypotheses that targeted patients in intervention clinics for whom the CV Wizard CDS tool results are viewed and / or printed will have significantly lower CVD risk scores and higher rates of CVD risk factor control, at visits in the year post-index visit period, compared to similar patients in control clinics, and compared to patients in intervention clinics for whom the tool alerted but was ignored at the index visit.

Analyses will be stratified by first-time and repeat patients to see if there is a difference in tool use as well as examine whether the time between visits effects tool use among repeat patients.

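### The treatment-on-the-treated analysis has two exposures, index-visit use and use counted over follow-up; nothing says which governs, and the counts partly reflect post-index risk

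*Combined protocol and SAP*

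**What the plan says.** Two parts of section 7.a describe the same named analysis.

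- **Quantitative Data.** ETOT is "limited to intervention CHC patients for whom the CV Wizard tool was used (results viewed / printed out) at the index visit". These patients are compared with Arm 1 patients for whom the tool was not used and, separately, with control-clinic patients. The hypothesis sentence that follows narrows the Arm 1 comparator: users are "compared to patients in intervention clinics for whom the tool alerted but was ignored at the index visit".
- **Effect of Treatment on the Treated Analysis.** Arm 1 patients are classed "in three categories of tool use (never used during follow-up, used once, used more than once", and each class is propensity-matched to control patients. On counting: "Counts of tool use will include use at index visit or subsequent study period visits, excluding the last visit". The analysis by quartile of baseline risk uses a collapsed form, "patients for whom the tool was ever used during follow-up, matched to controls as described above". The matching variables include the baseline value of the outcome, the "count of ambulatory care visits post-index" visit and the time from index to last visit. Linear mixed models are named for all outcomes.

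Three other provisions bear on the counts. Section 6.a (Programming CV Wizard to Accept OCHIN Data) has programmers "create the alert to prompt CDS use in targeted patients". Section 5.b defines targeting by reversible risk above 10%, or by diabetes or existing ASCVD with an uncontrolled factor (or a high A1c with diabetes), and allows manual runs for any adult. Inclusion in Aim 1 analyses needs an index visit and "at least one additional visit at a study clinic in the 12-month post-index visit period".

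**The concern.** ETOT is the plan's estimate of the tool's impact when it is used, as distinct from its population-level impact. Two definitions under one name form different groups and different contrasts. An Arm 1 patient with no use is a comparator in one place and a class matched to controls in the other. With no statement of precedence, the choice could be made after results are seen, or a stated hypothesis could go untested.

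The count definition raises a second question. Whether a patient ends up as never, once or more than once is settled during follow-up, while the outcome is evolving. If a later alert depends on risk at that visit, the groups are partly sorted by intermediate values of the outcome. A difference from controls could then appear for a tool that does nothing.

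**Working it through.** The documents give no sample size, effect or power figure for ETOT, so there is no stated number to reproduce.

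**1. The two texts side by side**

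| Element | Quantitative Data | ETOT section |
|---|---|---|
| Exposure | Viewed or printed at index | Never / once / more than once, over index and later visits except the last; ever used for the quartile analysis |
| Arm 1 non-users | Comparator | A class matched to controls |
| Comparators | Arm 1 non-users; controls | Controls only |
| Confounding control | None stated | Propensity matching to controls |
| Model | None stated | Linear mixed model |

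Neither text refers to the other or is labelled primary or sensitivity.

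**2. How the counts pick up post-index risk**

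Take a patient alerted at index with two post-index visits, so that index and visit 1 count and the last does not. Let *p* be the chance of use at an alerted visit, with no use otherwise. *p* = 0.5 is an assumption.

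| Class | Alerted at visit 1 | Not alerted at visit 1 |
|---|---|---|
| Never | (1−p)² = 0.25 | 1−p = 0.50 |
| Once | 2p(1−p) = 0.50 | p = 0.50 |
| More than once | p² = 0.25 | 0 |

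Patients not alerted at visit 1 are twice as likely to be classed never (0.50 / 0.25 = 2), and every patient classed more than once was alerted at visit 1. Matched controls are a mixture of both columns. Visit-1 risk correlates with last-visit risk, so matching on the baseline outcome, visit count and time to last visit leaves this sorting in place. For a zero-effect tool and this mechanism alone, never looks better and more than once looks worse. Once can go either way: 2p(1−p) exceeds p only when p is below 0.5.

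There are two limits. With a single post-index visit, excluding the last visit makes the count equal to index-visit use, and the mechanism vanishes. It also vanishes if use does not depend on alerts.

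**3. Illustrative size, alert mechanism alone (simulation A, true effect zero)**

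Inputs from the documents: SD 9.1 and correlation 0.2. Both come from the supplement's power statement, not Aim 1. Assumed: gamma-distributed risk with mean 15; drift −0.5 per visit; 1 + Poisson(2) post-index visits, capped at 8, so e⁻² = 13.5% have one; 50% use when risk is above 10; index risk above 10 only. Bias = mean change in the class minus mean change of patients with the same baseline risk and visit count, in risk points (negative = apparent improvement).

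Overall: never −0.50, once −0.23, more than once +0.73.

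| Post-index visits | Never | More than once |
|---|---|---|
| 1 | about 0 | nobody can be in this class |
| 2 | −0.38 | +0.82 |
| 3 | −0.78 | +0.80 |
| 4 | −1.15 | +0.77 |

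Across 54 combinations of correlation (0.2 to 0.8), use (20% to 80%), share of patients always alerting (0 to 70%) and off-alert use (none or half the alert rate), never ranged from −1.42 to −0.01 and more than once from +0.04 to +1.28. Adding the number of would-have-alerted visits to the matching brought all three classes to between −0.05 and +0.07, which identifies the alert path as the cause. That is a check for a zero-effect tool only; with a real effect it would condition on a mediator.

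**4. Adding provider choice**

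In simulation A, an unmeasured factor was given an odds ratio of 1.5 per SD for use. When it lowers later risk by 0.5 point per SD, the direction in step 3 holds in 32 of 54 scenarios, reverses in 10 and is mixed in 12. At 1.0 point the figures are 18, 23 and 13.

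Simulation B used different assumptions: index plus three visits, mean 14, SD 9.1, patient-specific trends, and 2% use without an alert. Strong selection means a factor that raises the log-odds of use by 1.0 per SD and lowers risk by 1.0 point per visit per SD.

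| Use when alerted | 0.2 | 0.4 | 0.6 |
|---|---|---|---|
| Alert only: never | −0.38 | −1.01 | −2.19 |
| Alert only: more than once | +1.00 | +1.00 | +0.94 |
| Alert only: index-visit use | 0.00 | 0.00 | +0.01 |
| Strong selection: never | +0.84 | +1.17 | +1.34 |
| Strong selection: more than once | −1.55 | −0.78 | −0.22 |
| Strong selection: index-visit use | −1.95 | −1.44 | −1.04 |

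In simulation B, 22% to 33% of patients with index risk above 10 are users by count but non-users at index, so the two definitions do form different groups.

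**The case against.** The ETOT section carries the title and gives the classes, counting rule, matching variables and model, so a normal reader would take it as operative. The earlier text is an overview that speaks of analyses in the plural, so the two could coexist. This has force, but no sentence says either thing. If the ETOT section governs alone, the contrast with ignored alerts is stated as a hypothesis and then left without confounding control.

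The ETOT section also has real safeguards: the last visit is not counted, and visit opportunity and baseline outcome are matched. These reduce the problem without removing it once a patient has two or more post-index visits. Manual runs and the diabetes and ASCVD routes loosen the link between current reversible risk and use. With 70% of patients always alerting and half-rate off-alert use, no count class was off by more than 0.09 point.

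The strongest objection is that index-visit use is no cleaner. It stands: under strong selection in simulation B, index-visit use was further from zero than more than once at every use rate.

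A reader might infer that index-visit use is the exposure in the ETOT hypotheses. It is not: the hypothesis sentence gives no timing for use, and index timing is in the analysis sentence before it. A reader might also infer that the within-Arm-1 comparison has no method at all. A linear mixed model is named; what is missing is control of confounding.

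**Conclusion.** The inconsistency is in the text and rests on no simulation: two exposures and two sets of comparators under one name, unranked. That the count groups partly reflect intermediate outcome values follows from the alert rule and the counting rule, provided use responds to alerts and patients have at least two post-index visits.

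The direction and size of the net bias cannot be known from the documents, because they do not give the alert mix, use pattern, visit numbers or strength of provider selection. The simulations are illustrative. They show either sign, from near zero to more than 1.5 points, against a smallest examined difference of 1.5% in the power statement. They cover only index risk above 10, not the lower-risk stratum that the plan also analyses.

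A reader might go further and conclude that the counts will make the tool look harmful, that any bias must be smaller than the effects of interest, or that index-visit use is less biased. None of these is supported. A count-based difference could not be read as benefit or harm from use. The intent-to-treat comparison is unaffected.

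**What to change.** Reconcile the two parts of section 7.a.

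1. State that index-visit use (viewed or printed), with both comparators, is the exposure for the ETOT contrasts set out under Quantitative Data. The reason is that it is the analysis definition given there and is fixed before follow-up, not that it is less biased. Settle whether the Arm 1 comparator is all non-users or those whose alert was ignored.
2. Match these contrasts on variables known at or before index, leaving out post-index visit count and time to last visit. Apply the same propensity approach to the within-Arm-1 comparison.
3. Keep the never / once / more-than-once and ever-used analyses, labelled exploratory and not interpreted as effects of use. Alternatively, model use as time-varying with risk and alert status at each visit; the plan already calculates risk at every encounter.
4. State that both exposures remain open to confounding by provider choice.

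The cost is SAP wording and a re-run of matching on existing data. The time-varying option also needs would-have-alerted status derived for controls. The drawback is dilution: index visits fall in the first 6 months while implementation support runs for 18 (section 6.b), so patients first using the tool later count as unexposed.

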characteristics	visit or insurance type through study period; # visits to that site / provider in last	
	year; whether visit was with patient's primary care provider; provider type. Others	
	TBD based on input from clinician advisors.	
Other patient comorbid	Renal function: diagnosed with end stage renal disease or chronic kidney disease;	
conditions	Charlson Comorbidity Score (Modified): Indicator of serious comorbid conditions	
	that may shorten life expectancy, modified to exclude CV components; depression	
	296.xx, 311.xx diagnosis. Other relevant comorbidities TBD.	
Visit type	New patient or established patient	
Provider type	Provider type (PCP or other); # in patient panel	
Other clinic factors	See Table 5; data from baseline survey	
CVD care / process	Measurement	

Recommended care	Whether care suggestions were acted on within 7 days of the encounter; e.g., if CV
that is ordered.	Wizard suggests starting a statin, we will ask whether a prescription was issued.

#### b. Study Aim 2 & 3

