## **Secondary Analyses**

Secondary analyses will examine use of the CV Wizard CDSS (main outcome). We will assess which patient-, encounter-, provider-, and clinic-level characteristics are associated with use of the CDS at eligible encounters. Additional analyses will explore the impact of CDS system use on prescribing pattens targeting CVD risk as well as the influence of system prioritization recommendations on risk factor management. We will also analyze results from a provider survey conducted to assess reasons for CV Wizard use and non-use.

Quantitative data will be derived from the CDS data repository and extracted EHR data. Provider survey data was collected from 44 study clinic clinicians conducted midway through the study period.

For quantitative analyses, descriptive statistics will show patient and encounter characteristics included in analyses. After exploring the distribution of the outcome variables to identify the most appropriate model, multilevel models with random effects for provider and clinic will be used to assess (1) multi-level characteristics associated with CV Wizard use and (2) the association between system use and system prioritization on CVD risk factor management.

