#### Additional Information about Sensitive Data

We plan to pull data related to mental health diagnoses (depression, anxiety, and severe mental illness) to determine whether it explains variance in CV Wizard tool use. This data will be pulled

from the EHR (i.e., this information will *not* be collected directly from patients that are participating in the qualitative interviews). We will follow the same safeguards for this sensitive data as we do for all data collected in this study (see sections on data management, sharing, and protection; confidentiality; and security). This data will be collected (as applicable) for all clinics participating in the study. Given that individual patients are not enrolled for this aim of the study, there is no consent form or PRA to which this information should be added. NOTE: Each OCHIN member clinic has business use agreements with OCHIN to handle and manage PHI from their clinical data, and each CHC agrees that their electronic health record data may be used in research as part of their membership agreement.

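### The treatment-on-the-treated match omits index CVD medication, diabetes and ASCVD status, so its tool-use estimates may be confounded in an unknown direction

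*Combined protocol and SAP*

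**What the plan says.** The section Effect of Treatment on the Treated Analysis sets up the comparison: "We will match intervention organization patients in three categories of tool use (never used during follow-up, used once, used more than once"), each category being matched to patients of control organizations. The list of variables begins "Matching variables will include age, FPL, outcome of interest at baseline, race / ethnicity, sex". It continues with the number of ambulatory visits after the index "visit, time from index visit to last study period visit, and clinic rural / urban status". That makes eight variables. On method it says: "Propensity scores will be estimated using nearest-neighbor matching with replacement". It gives no caliper, balance criterion or balance report.

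Other sections bear on the list:

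- Section 5.b (Inclusion and Exclusion Criteria) gives three routes by which the tool targets a patient: reversible risk above 10%, diabetes with an uncontrolled factor or high A1c, and ASCVD with an uncontrolled factor.
- Secondary Outcome Measures defines adoption by the care team's choice to run the tool.
- Intent to Treat Analysis says that diabetes raises estimated reversible risk even when risk factors have been addressed. For that reason it excludes patients newly diagnosed during follow-up from the reversible-risk analyses.
- Programming CV Wizard to Accept OCHIN Data lists the extracted fields: "medication, laboratory, diagnostic/problem list codes, vitals, smoking".
- Table 6 lists potential covariates, among them "Charlson Comorbidity Score (Modified): Indicator of serious comorbid conditions", insurance, visits in the prior year, and new versus established patient.
- Secondary Analyses will examine which patient, encounter, provider and clinic "characteristics are associated with use of the CDS at eligible encounters".

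**The concern.** Randomisation protects the comparison of arms. It does not protect a comparison of the Arm 1 patients for whom someone chose to open the tool with patients in Arm 2. There the match has to make the groups comparable.

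The tool is meant to work by prompting treatment to be started or changed. Two patients with the same baseline score, one already on treatment and one not, have different room for that to happen. Clinicians might open the tool more often for untreated patients, or more often for treated patients who are already engaged in care. Diabetes and ASCVD could likewise influence both the decision to use the tool and the later course of the score. If so, part of an estimated effect of use is selection. Because users and never-users are selected in opposite directions, the never/once/more-than-once contrast could also resemble a dose response without being one.

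**Working it through.** **Is the omission real?** Index CVD medication, diabetes, ASCVD and eligibility route are absent from the eight matching variables, and no other section adds them to the match. The later linear mixed models do not clearly close the gap. The ETOT section names no adjustment covariates for them. The ITT adjustment set (age, race/ethnicity, gender, rural/urban status, poverty level, visit count, follow-up time) would not supply these factors even if it were carried over.

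**Does the plan treat them as relevant elsewhere?** It does for diabetes. The ITT section removes incident diabetes from the reversible-risk analyses, but prevalent diabetes is left unbalanced in ETOT. The Supplement Addendum, also a non-randomised comparison, lists diabetes at index as a potential covariate.

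**How large could the bias be?** The plan gives no figure for this match, so there is nothing to reproduce. For one omitted binary factor,

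bias = (effect of the factor on change) × (difference in its prevalence left after matching).

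To see what imbalance matching might leave, nearest-neighbour propensity matching with replacement was simulated with a true tool effect of zero. Every input is an assumption: 6,000 patients per arm, factor prevalence 40%, the factor raising the baseline score by 2 points, and matching on age and baseline risk as a stand-in for the full list. The factor was taken to make use more likely and to give a larger later fall.

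| Odds ratio of factor for use | Imbalance left (percentage points) | Spurious benefit, 1-point effect | Spurious benefit, 3-point effect |
|---|---|---|---|
| 1 | about 0 | −0.03 | 0.03 |
| 1.5 | about 8 | 0.09 | 0.25 |
| 2 | about 13 | 0.13 | 0.43 |
| 3 | 19 to 20 | 0.14 | 0.57 |

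The formula gives similar values: 3 × 0.079 = 0.24, 3 × 0.129 = 0.39, 3 × 0.192 = 0.58, and for a 1-point effect 0.08, 0.13 and 0.20. The two agree to within about 0.06 points, roughly the simulation noise.

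With the factor added to the match, the imbalance was about 0 and the bias within about 0.05 points in every scenario. If the factor made use less likely, or went with a smaller fall, the sign would reverse. Several omitted factors could add up or cancel.

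**The case against.** The strongest reply is that the plan already has safeguards.

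- It matches on the baseline value of the outcome.
- It stratifies reversible-risk analyses at 10%. If this means reversible risk, an automatically targeted patient in the lower stratum must have entered through diabetes or ASCVD, so part of the eligibility route is separated out.
- It adds baseline-risk quartiles among ever-users.
- It restricts the other outcomes to patients uncontrolled at baseline, which for A1c largely deals with diabetes status.
- It matches never-users to controls as well, and a divergence there would signal selection.
- The Quantitative Data section describes users against non-users and Arm 2, and mentions stratifying by first-time and repeat patients.

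This narrows the point but does not remove it. The lower stratum does not tell diabetes from ASCVD, and the upper one mixes all three routes. None of these steps balances medication. The descriptive comparisons are not said to feed the match. The never-used group can reveal selection but does not correct it.

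Some stronger readings are tempting and not supported:

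- *The matched controls are dissimilar.* The documents contain no balance data. This is a well-founded risk, not a finding.
- *The bias approaches the smallest effect of interest.* Statistical Power examines differences of 1.5, 2 and 3 points for the comparison of arms and does not call any of them that. A bias as large as 1.0 point needs, for example, a 20-point imbalance and a 5-point effect (0.20 × 5 = 1.0), and neither input comes from the documents.
- *Every collected predictor of use belongs in the match.* Table 6 calls its items potential covariates. Mental-health diagnoses are collected "to determine whether it explains variance in CV Wizard tool use", which concerns use and not outcome. A variable that predicts only use can cost precision without removing confounding. Provider factors would first need a counterpart in control clinics.

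**Conclusion.** The point holds for the ETOT analysis only. The match leaves out index CVD medication, diabetes status and ASCVD status, which plausibly relate both to the decision to use the tool and to later change in risk. The existing safeguards remove part of the resulting confounding, not all of it. The ETOT estimates and the contrast across use categories may be biased, and the documents do not show in which direction.

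The size is likewise unknown from the documents. About 0.1 to 0.6 points is an illustration that rests on one omitted factor at 40% prevalence, an odds ratio for use of 1.5 to 3 and a 1 to 3 point effect on change. If the factor does not predict use, the bias is essentially nil. A reader might take this as a flaw in the trial's main result. It is not, because the ITT analysis compares all targeted patients by randomised arm and does not depend on this match.

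**What to change.** In Effect of Treatment on the Treated Analysis, extend the propensity model with these variables, all measured at or before the index visit:

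- diabetes status and ASCVD status;
- use of each CVD drug class;
- the baseline covariates already listed in Table 6 that are expected to relate to outcome: modified comorbidity score, insurance, prior-year visit count, and new versus established patient.

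Report standardised differences for all matching variables after matching, separately for each tool-use category, and adjust the outcome model for any that remain imbalanced.

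The cost is a change of SAP wording and some programming. Medication and diagnosis data are already extracted from the EHR for the tool, but Table 6 does not list drug class or ASCVD status as analysis covariates, so their definitions must be written and programmed. With more variables in the score, some matches may be slightly less close.
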